INVASIVE

INFLUENCE OF PRENATAL COUNSELING IN INVASIVE TESTING

PROTOCOL FOR A RANDOMIZED CONTROLLED TRIAL

[name]

[name]

[name]

[name]

Hospital Clinic of Barcelona / University of Barcelona

Study Number: IRN2019/03/0001

Human Subjects Review Approval: HCB/2019/0788

September 15th, 2019

Study design:

This is a randomized open-label controlled trial evaluating the impact of an extra 15-minute prenatal counseling before the first trimester combined screening test for Down's syndrome, on the women's attitudes and preferences towards having an invasive testing as the first line option for screening of chromosomal abnormalities.

Data will be collected by the study-site manager and stored in an electronic data-capture database. The coordinator of the study and the statistician will witness the accuracy of the data at the beginning, middle, and end of the study (on-site audit). Data will be captured in a paper form basis and then captured into the electronic database.

Participants

Inclusion criteria: any pregnant woman of at least 18 years old, attending the first trimester combined screening test for chromosomal abnormalities (between 11+0 and 13+6 weeks' gestation). The exclusion criteria: women not willing to participate in the study, women without an answer in the question regarding which prenatal test would they choose (main outcome), or women with no sufficient knowledge of Spanish or Catalan to be able to read and understand the questionnaire.

Intervention and procedures

For the experimental group, the intervention will consist of an extra 15-minute prenatal counseling before their first trimester scan. This intervention will require an explanation of all screening techniques for chromosomal abnormalities, including the first trimester combined test, cfDNA testing, invasive testing, and no screening at all. The intervention will be given by a single maternal-fetal medicine specialist who will explain all pros and cons of all given methods, giving also time to solve any question the woman may have. After the intervention (counseling), all participants will be asked to fill a questionnaire of twenty-one question regarding their knowledge, attitude and preferences about prenatal testing.

For the control group, women will not be given an extra 15-minute counseling (no intervention), but will be directly asked to fill the questionnaire about their knowledge, attitude and preferences about prenatal testing.

Sample size

Sample size calculation has been made using an independent two-sample proportions likelihood-ratio test. We expect a 10% of women willing to have an invasive procedure as a first line test for aneuploidies in the control group, and a 25% difference to those in the experimental group that are given an extra 15-minute prenatal counseling, this yields a sample of 42 women per arm with a total of 84 subjects using a Type I error of 0.0501 and a power of 80% by a two-sided test.

Randomization and intervention

Participants will be randomized using an interactive Web-response system assigning patients in a 1:1 ratio to receive the extra counseling before first trimester assessment (intervention group) or nothing (control group). The allocation will be performed by the study manager. The maternal-fetal medicine specialist will be in charge of the participant's enrolment and will also perform the intervention to the corresponding randomized group. This is an open-label study which means that the specialist and women will be aware of the allocation and intervention every time.

Follow-up after the intervention

After both groups (the experimental and control) have filled the questionnaire, the routine prenatal care will be given according to our hospital's guidelines, which consists of a first trimester ultrasound scan, and the subsequent risk calculation for trisomy 21 and 18 with the use of the first trimester combined test. In case of risk greater than 1/250, an invasive diagnostic test will be offered. For risks between 1/250 and 1/1,000 a complementary first trimester genetic sonogram using secondary markers (nasal bone, tricuspid regurgitation, and ductus venosus) will be offered to re-calculate the risk for Down's syndrome. For women with Down's risk greater than 1/1000, no further evaluations will be offered.

Questionnaire

The questionnaire consists of twenty-one questions assessing the knowledge, preferences and attitude towards prenatal testing in the first trimester of pregnancy. The questionnaire will be divided in two parts.

The first fourteen questions consist of demographic characteristics and obstetrics history, such as age, ethnicity, study level, marital status, religion, salary, employment, parity, previous miscarriages, previous terminations of pregnancy, previous congenital defects, pregnancy search time in months, type of conception, and who had provided any type of previous information about prenatal screening/testing. Women will be asked to select only one option for each question. All questions will have the possibility to answer as “Prefer not to answer”. The second part of the questionnaire will assess the preferences and attitudes towards prenatal testing; women will be asked to choose only one option for each question. The following questions will be included in the second part of the questionnaire: What influences you the most about prenatal testing? Who influenced you the most about prenatal testing? Would you like to choose your prenatal test? Which prenatal test would you choose? What is your opinion about termination? All questions include an “I don’t know answer”. The two final questions will ask the following, “What information regarding the results of prenatal testing is more important for you?” and “What is most important for you about prenatal testing?”. Women will be asked to score the first question from 1 to 5, meaning 1 the least important and 5 the most important, and from 1 to 6 in the same manner for the second question. These two questions will be assessed as means, where the question with the highest mean represents what is most important for the patient.

Outcomes

The primary outcome of the study is the desire to choose an invasive diagnostic testing as the first option of screening for chromosomal abnormalities. This will be measured in the questionnaire by asking the question: which prenatal test would you choose if given the opportunity? Women will be asked to choose only one answer between first trimester combined test, cell-free DNA, invasive testing.

Statistical analysis

Analysis will be conducted by intention-to-treat. Missing data for the main outcome will be handled by complete-data analysis because women without an answer on the main outcome will be excluded. All analyses will be divided by groups (control vs experimental group). Continuous data will be assessed for normality using the Kolmogorov-Smirnoff test. Normally distributed variables will be compared using t-test and expressed as mean and standard deviation (SD), while not normally distributed variables will be analyzed using the Mann-Whitney-U test and expressed as medians and interquartile range (IQR). Quantitative variables will be

compared using X^2 test and expressed as numbers (n) and proportions (%). For the main outcome, preferences for prenatal testing among groups will be analyzed using absolute risk increase defined as the incidence of the outcome in the experimental group minus the incidence in the control group. The absolute risk increase will be depicted in a forest plot. A multivariate logistic regression will be performed to determine the Odds for choosing an invasive testing adjusting by demographic characteristics and previous counseling. Data will be analyzed using STATA v.15.3 for Mac (Texas College Station) and GraphPad Prism version 8.1.2 for Mac, GraphPad Software, San Diego, California USA, www.graphpad.com.

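### Women who leave the primary question unanswered are excluded after randomisation, so the primary comparison is a complete-case analysis and not the intention-to-treat analysis the plan claims

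*Combined protocol and SAP*

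**What the plan says.** - **Participants.** Among the exclusion criteria are "women without an answer in the question regarding which prenatal test would they choose (main outcome").
- **Intervention and procedures.** In the experimental arm the questionnaire comes after the intervention: "After the intervention (counseling), all participants will be asked to fill a questionnaire". Controls go straight to the questionnaire.
- **Statistical analysis.** "Analysis will be conducted by intention-to-treat". The next sentence reads: "Missing data for the main outcome will be handled by complete-data analysis because women without an answer on the main outcome will be excluded". The effect measure is the "absolute risk increase defined as the incidence of the outcome in the experimental group minus the incidence in the control group"; the denominator of each incidence is not defined.
- **Questionnaire and Outcomes.** Straight after listing the second-part questions, which include the primary one, the plan says "All questions include an “I don’t know answer". The outcome definition is narrower: "Women will be asked to choose only one answer between first trimester combined test, cell-free DNA, invasive testing".
- **Sample size.** 42 women per arm, 84 in total, for an expected 10% in controls and a difference of 25 points. No allowance for unanswered primary questions is stated.

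**The concern.** An eligibility criterion has to be decidable before allocation. This one depends on the outcome questionnaire, so it acts as a post-randomisation exclusion. Counselling explains the options and gives time for questions, so it could change who is able or willing to answer. Women who drop out of the denominator may then differ between arms, and randomisation no longer protects the comparison of those who remain.

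Two things are at stake. The result would carry an intention-to-treat label that its analysis does not earn. And the plan provides neither a report of missing answers by arm nor any sensitivity analysis, so a reader could not judge whether the exclusion mattered. If women are excluded as ineligible, they may not appear in the participant flow at all.

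**Working it through.** **1. The plan's own figure.** Inputs from Sample size: 10% vs 35% (10% plus 25 points), two-sided type I error 0.0501, 80% power, likelihood-ratio test, 1:1 allocation. Power is the probability that a noncentral chi-square with 1 df exceeds its critical value, with noncentrality n × 2[f(0.10) + f(0.35)], where f(p) = p ln(p/0.225) + (1−p) ln((1−p)/0.775) and 0.225 is the mean of the two rates. The factor is 0.1876. At n = 42 the noncentrality is 7.88 and power is 80.2%. The stated 42 reproduces; the arithmetic is not at fault.

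**2. Power if only answerers are analysed** (non-answer rates are assumptions, equal in both arms):

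| Non-answer | Answerers per arm | Power |
|---|---|---|
| 5% | 42 × 0.95 = 39.9 | 78.1% |
| 10% | 42 × 0.90 = 37.8 | 75.9% |
| 20% | 42 × 0.80 = 33.6 | 70.9% |

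**3. Bias of the complete-case comparison when counselling has no effect.** Let p be the true share wanting invasive testing (same in both arms), q the non-answer rate, and r the share of non-answerers wanting invasive testing (same in both arms). The share among answerers is (p − qr)/(1 − q). Assume q = 10% in controls and 5% after counselling.

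- p = 10% (the plan's control rate), r = 0: 0.10/0.95 − 0.10/0.90 = 10.53% − 11.11% = −0.6 points. With r = 10% the bias is 0. With r = 20% it is 0.09/0.95 − 0.08/0.90 = 9.47% − 8.89% = +0.6 points.
- p = 20% (an assumption), r = 0: 0.20/0.95 − 0.20/0.90 = 21.05% − 22.22% = −1.2 points. With r = 20% it is 0. With r = 40% it is 0.18/0.95 − 0.16/0.90 = 18.95% − 17.78% = +1.2 points.

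The bias can go either way, and it vanishes when non-answer is unrelated to preference.

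**4. Bounds over all 42 randomised per arm.** Assume 4 controls and 14 counselled women choose invasive testing, close to the planned 10% and 35%. The lower bound counts every missing control as wanting invasive testing and no missing counselled woman as wanting it; the upper bound does the reverse. P-values are from the likelihood-ratio test, which the plan names for its sample size.

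| Missing (control, counselled) | Complete case | Lower bound | Upper bound |
|---|---|---|---|
| 2, 2 | 14/40 − 4/40 = 25.0 (p=0.006) | 14/42 − 6/42 = 19.0 (p=0.038) | 16/42 − 4/42 = 28.6 (p=0.002) |
| 3, 2 | 14/40 − 4/39 = 24.7 (p=0.007) | 14/42 − 7/42 = 16.7 (p=0.076) | 28.6 (p=0.002) |
| 6, 2 | 14/40 − 4/36 = 23.9 (p=0.012) | 14/42 − 10/42 = 9.5 (p=0.33) | 28.6 (p=0.002) |

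Differences are in percentage points. The lower bound depends only on the number of missing controls. Two leave the conclusion intact; three do not.

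**The case against.** The strongest reply is that much of this is labelling. The complete-data rule is disclosed twice, and intention-to-treat can be read loosely as analysis in the assigned arm. The remedy also keeps the answerers-only comparison as primary, so its estimate barely changes. That is fair as far as it goes. What stands is that an outcome-dependent exclusion cannot be an eligibility criterion, and that the plan gives the reader no means of judging its effect.

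A second reply is that little will be missing. The questionnaire follows counselling or enrolment directly, before routine care, so there is no follow-up period in which to lose women. The worst-case bound with three missing controls also needs all three to want invasive testing, when the plan expects 10%. Both points are right: the bounds are extremes, not expected bias.

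Three stronger readings should be resisted.

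- A reader might infer that the primary result will be materially biased. Nothing in the documents gives a non-answer rate or shows that it differs by arm.
- A reader might infer that the denominator is wholly undefined because of undecided women. The plan calls that option an answer and excludes only women without one, so on a literal reading they stay in. The gap is that Outcomes lists only three tests.
- A reader might infer an uncoded refusal option on the primary item from "All questions will have the possibility to answer as “Prefer not to answer". That sentence sits in the description of the first fourteen questions, and the second part has its own option. The questionnaire form is not in the documents, so the point cannot be pressed.

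**Conclusion.** The point holds and should be fixed, but it is not shown to threaten the trial's conclusion. What is certain from the text is that the exclusion takes place after randomisation, depends on the outcome, and contradicts the intention-to-treat claim. The bias is of unknown direction and size. It is zero if non-answer is unrelated to preference, and reaches 0.6 points (10% true rate) or 1.2 points (20%) under the assumed 10% vs 5% non-answer and the ranges of r shown. The reason to act is fragility at this sample size: under the assumed 4 vs 14, three unanswered control questionnaires out of 42 are enough for the worst-case bound to lose significance. The loss of power is modest at low non-answer rates and rests on assumed rates throughout. The coding of an undecided answer is a minor clarification.

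**What to change.** 1. **Participants:** delete the no-answer item from the exclusion criteria.
2. **Participant flow:** keep every randomised woman in her assigned arm and report missing primary answers by arm.
3. **Statistical analysis:** describe the primary absolute risk increase as an analysis of women who answered, and do not call it intention-to-treat.
4. **Sensitivity analyses over all randomised women:** best-case and worst-case bounds, and missing counted as not selecting invasive testing. The latter should not become primary, because it can create an effect. With a true 20% in both arms and non-answer of 10% vs 5% unrelated to preference, it gives 0.20 × 0.95 − 0.20 × 0.90 = +1.0 point.
5. **Outcomes:** state that an undecided response is an answer that does not select invasive testing.
6. **Sample size:** leave it at 84, and state that 80% power assumes all 42 per arm answer, falling to about 78%, 76% or 71% at an assumed 5%, 10% or 20% non-answer.

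**Cost:** wording changes and a little more analysis, with no extra women because 84 stands. The primary result loses its intention-to-treat label, any shortfall in power is accepted openly, and the bounds may be wide (9.5 to 28.6 points in the example with 6 and 2 missing).

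### The item on previous information is answered after counselling in the experimental arm only, so the previous-counselling covariate could depend on allocation; giving part one before randomisation removes the doubt cheaply

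*Combined protocol and SAP*

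**What the plan says.** The plan describes one form of 21 questions. Under Intervention and procedures, the experimental arm receives it once the 15-minute session is over: "After the intervention (counseling), all participants will be asked to fill a questionnaire of twenty-one question". The control arm has no session and "will be directly asked to fill the questionnaire about their knowledge, attitude and preferences about prenatal testing".

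The Questionnaire section states: "The questionnaire will be divided in two parts". The first fourteen questions cover demographics and obstetric history, and the last of those listed asks "who had provided any type of previous information about prenatal screening/testing". On answering, the section says: "Women will be asked to select only one option for each question". No section says that part one is given before randomisation or before counselling.

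Under Statistical analysis, the main outcome is analysed by an "absolute risk increase defined as the incidence of the outcome in the experimental group minus the incidence in the control group". A multivariable logistic regression for choosing invasive testing is also planned, "adjusting by demographic characteristics and previous counseling". The plan does not define the previous-counselling term.

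**The concern.** A covariate in an adjusted treatment comparison should be fixed before allocation or be unable to respond to it. This item is recorded after randomisation in both arms, and after exposure to the intervention in one. A woman who has just spent 15 minutes with a specialist going through every testing option might name that specialist as her source. Because only one answer is allowed, doing so would also displace her true earlier source.

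Three things could follow:

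- The covariate becomes correlated with arm, and the adjusted odds ratio loses precision.
- If women whose choice was changed by the session name it more often, or if true prior information predicts the outcome, the adjusted odds ratio is also pulled towards 1.
- The row for this item in the group comparison could show an imbalance that randomisation did not produce.

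The other thirteen part-one items (age, parity, education and so on) are unlikely to be changed by a short conversation.

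**Working it through.** **1. The plan's own figure.** Inputs from Sample size: 10% in controls, a difference of 25 percentage points (so 35%), two-sided, 80% power, likelihood-ratio test. Let h(p) = p ln p + (1−p) ln(1−p).

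- h(0.10) = −0.3251, h(0.35) = −0.6474, and at the mean proportion h(0.225) = −0.5332.
- d = 2 × [(−0.3251 − 0.6474)/2 + 0.5332] = 0.0938.
- With n = 42 per arm, √(2 × 42 × 0.0938) = 2.807, and power = Φ(2.807 − 1.960) = 80.2%.

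The planned 42 per arm is reproduced, at alpha 0.05 or at the stated 0.0501. The odds ratio implied by 35% versus 10% is (0.35/0.65)/(0.10/0.90) = 4.85.

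**2. Effect on the adjusted odds ratio.** The following inputs are assumed, because the documents do not give them:

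- Each woman has a 10% chance of choosing invasive testing without counselling. Counselling moves a further 25% of all women.
- A share q truly had prior information, equal in both arms and unrelated to the outcome. Coding is yes/no.
- A share c of experimental women without prior information name the session (crediting). Women moved by the session do so 1.4 times as often, capped at 100%.
- Model: outcome on arm and covariate, Wald test at 5%, 20,000 runs per setting. Monte Carlo error is √(0.78 × 0.22/20,000) ≈ 0.3 percentage points.

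Power, with median odds ratio in brackets:

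| Crediting c | q = 30% | q = 50% | q = 70% | q = 90% |
|---|---|---|---|---|
| 0-10% | about 78% (5.2) | about 78% (5.2) | about 78% (5.2) | about 78% (5.2) |
| 25% | 75% (5.0) | 77% (5.1) | 77% (5.1) | 78% (5.2) |
| 50% | 64% (4.6) | 71% (4.8) | 74% (5.0) | 77% (5.1) |
| 75% | 38% (3.7) | 57% (4.3) | 69% (4.8) | 76% (5.1) |

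The mean absolute risk increase is 0.25 in every cell. A separate run of 4,000 per setting gave the same picture.

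**3. Sensitivity to the assumptions.**

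- *Crediting unrelated to outcome:* the odds ratio stays at 5.1-5.2. Power at 75% crediting is 63/68/73/76% for q = 30/50/70/90%.
- *Overall crediting held at 75%, with the 1.4-fold difference kept:* power is 44/61/70/76%.
- *Very low prior information (q = 10%):* power is 71/50/13% and the odds ratio 4.8/4.1/2.5 at 25/50/75% crediting.
- *Three-category coding (none, professional, other), session recorded as professional:* with a true professional source in 30/50/70%, power is 75/77/77% at 25% crediting, 63/70/74% at 50% and 37/55/68% at 75%. This nearly matches yes/no coding.
- *Prior information predicts the outcome:* this is a large-sample calculation with q = 20% or 40%, a covariate odds ratio of 2 or 4, and the same crediting rate whatever the outcome. The true conditional odds ratio is 4.96 to 5.49. The model returns 4.69 to 4.96 at 10% crediting, 4.17 to 4.54 at 25% and 3.66 to 4.23 at 50%. Attenuation therefore starts earlier than in the table if the covariate is prognostic.

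**4. Effect on the group-comparison row.** The recorded proportion is q in controls and q + (1−q)c in the experimental arm. With q = 30% and c = 25%, this is 0.30 versus 0.30 + 0.70 × 0.25 = 0.475. The chance that the chi-square test for this row is significant, with 42 per arm and crediting unrelated to outcome, is:

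| Crediting c | q = 30% | q = 50% | q = 70% | q = 90% |
|---|---|---|---|---|
| 0% | 5-6% | 5-6% | 5-6% | 5-6% |
| 25% | 40% | 24% | 12% | 8% |
| 50% | 92% | 68% | 39% | 15% |

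This row reacts at crediting rates that leave power almost unchanged.

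**The case against.** The strongest reply is that the mechanism rests on an item nobody outside the trial has seen. The protocol paraphrases it, and the paraphrase already points backwards in time. The session is described as extra, and part two has its own question about who influenced the woman most, which is a natural place to credit the session. The form itself may say that it means information before today. The link to the covariate is also inferred: the regression sentence speaks of counselling, while the item speaks of a source of information. Since that sentence does not name allocation as a term, it could be argued that it means the trial session itself. Finally, the damage is small unless many women misread the item, and the sample size was not set for the adjusted model.

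Most of this stands as a limit on size. Dependence on allocation is possible, not demonstrated; neither the crediting rate nor the rate of true prior information is documented; and the main analysis is untouched. It does not remove the point. No other listed item could supply the covariate, and calling the session that defines the arms previous counselling is a strained reading. The collection time is stated plainly, and it follows exposure in one arm only.

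**Conclusion.** The concern holds as a possibility. A covariate meant to describe the woman before the trial is collected after the intervention in one arm, and nothing in the documents rules out its being shaped by allocation. If prior information is unrelated to the outcome, the loss is nil at 0-10% crediting and small at 25%; a material loss needs both high crediting and low true prior information. If prior information is prognostic, the odds ratio is attenuated earlier. The baseline row could mislead at 25% crediting. All of these sizes rest on assumed rates. Exposure is confined to the adjusted odds ratio and that one row, so this is a low-severity improvement to the design, held with medium confidence.

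**What to change.** Have every woman complete questions 1-14 after consent and before randomisation, and questions 15-21 at the time now planned. State in Statistical analysis that only pre-randomisation answers serve as covariates, and name the item that defines previous counselling.

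The cost is handing out an existing two-part paper form in two steps at the same visit and linking the two parts for each woman. It needs no new question, staff or participant, and 42 per arm stands.

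If the form cannot be split, there are two fallbacks. One is to confirm, or word the item so, that it refers to information received before today's visit; this still relies on women separating earlier information from the session they have just had. The other is to leave the term out of the adjusted model, or report the model with and without it. The choice should be made before recruitment, because the timing cannot be repaired afterwards.

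### The highest-mean rule names a most important item with no interval, runner-up comparison or tie rule, and 42 women per arm cannot separate items that are close.

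*Combined protocol and SAP*

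**What the plan says.** The Questionnaire section describes two closing questions on what women value. For the scales it states "Women will be asked to score the first question from 1 to 5, meaning 1 the least important and 5 the most important" and, for the other question, "from 1 to 6 in the same manner for the second question". The analysis follows in one sentence: "These two questions will be assessed as means", "where the question with the highest mean represents what is most important for the patient". The section adds no interval, minimum lead, comparison between items or handling of ties.

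Statistical analysis adds that "All analyses will be divided by groups (control vs experimental group"). It also has a general rule for continuous data: a t-test with mean and SD if normal, Mann-Whitney with median and IQR if not. It does not say whether the 1-5 and 1-6 scores count as continuous.

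Sample size sets the arm size: "this yields a sample of 42 women per arm with a total of 84 subjects". The Outcomes section names only the choice of invasive testing; the two scored questions are not listed there.

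**The concern.** The sentence in the Questionnaire section is more than a way of presenting data. It says what may be concluded: the item with the largest sample mean is what matters most. A sample mean from about 42 women has sampling error, and the largest of five or six such means is partly the luckiest. If the real leaders are close, the rule can name the wrong one, and it reports a narrow lead in the same terms as a wide one.

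Results are produced by arm, so the rule can be applied once in each arm. Two arms with identical priorities can then show different top items. The Study design section frames the trial around women's attitudes and preferences, and these questions bear directly on that, so a mistaken statement about what women value would matter to readers.

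**Working it through.** **The plan's own figure.** The only computed figure is the sample size. Inputs from Sample size: "We expect a 10% of women willing to have an invasive procedure as a first line test for aneuploidies in the control group", a 25-point difference (so 10% against 35%), and "using a Type I error of 0.0501 and a power of 80% by a two-sided test". For a likelihood-ratio test, the noncentrality is λ = 2n[D(0.10) + D(0.35)], where D(p) = p ln(p/0.225) + (1−p) ln((1−p)/0.775) and 0.225 is the average of the two rates. At n = 41, λ = 7.69 and power is 79.2%. At n = 42, λ = 7.88 and power is 80.2%. So 42 per arm reproduces. It was set for the primary outcome, and no precision is stated for the scored items.

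**Assumptions.** The documents give no SDs, correlations, item means or item lists. I assume SD 1.2, between-item correlation 0.3, five or six items (read from the scale lengths), n = 42 per arm, and the same true means in both arms.

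**Precision of a lead.** Two items scored by the same women differ with standard error

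SE = SD × √(2(1−ρ)/n) = 1.2 × √(1.4/42) = 0.219.

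The 95% half-width is 2.02 × 0.219 = 0.44 points. For SD 1.0 to 1.2 and correlation 0 to 0.3 it runs from 0.37 to 0.53. An observed lead smaller than that is compatible with no lead.

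**Two leading items, others far behind.** An arm picks the true leader with probability p = Φ(lead/SE), and two independent arms disagree with probability 2p(1−p).

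- Lead 0.2: Φ(0.91) = 0.819; wrong item 18%; arms disagree 2 × 0.819 × 0.181 = 30%.
- Lead 0.5: Φ(2.28) = 0.989; wrong item 1.1%; arms disagree 2.2%.
- Lead 0: p = 0.5; arms disagree 50%.

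**All k items equal.** The arms disagree with probability 1 − 1/k: 80% for five items, 83% for six.

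**Simulation with all items present** (item means drawn from a multivariate normal with covariance SD²[(1−ρ)I + ρJ]/42):

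| True item means | Wrong item in an arm | Arms name different items |
|---|---|---|
| 4.0, 3.8, 3.5, 3.2, 3.0 | 18% | 30% |
| 4.0, 3.9, 3.8, 3.5, 3.0 | 39% | 54% |
| 4.2, 4.0, 3.9, 3.7, 3.4, 3.0 | 22% | 37% |
| 4.2, 3.7, 3.5, 3.2, 3.0 | 1% | 2.3% |
| 4.0, 3.4, 3.2, 3.0, 2.8 | 0.3% | 0.6% |

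**Sensitivity.** At zero correlation the first two rows rise to 36% and 58% disagreement. With uncorrelated scores, a 0.5-point lead and SD from 1.0 to 1.7, disagreement runs from 2% to 45%, depending also on how many rivals are close.

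If women must rank the options, item means have to sum to 15 (five items) or 21 (six), and the table does not apply. In a forced-ranking simulation with two close leaders, the arms disagree about 34 to 35% of the time at a lead of 0.22 to 0.25 points, and about 6% at 0.50 to 0.59. With one leader over equal rivals, they disagree 19 to 21% at a lead of 0.61 to 0.73, and about 1% at 0.95 to 1.14. Exact ties for the top mean occur in about 3% of arms when two items lead equally and 5 to 6% when all items are equal.

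**The case against.** A reader might infer that the plan will treat different top items in the two arms as an effect of counselling. The documents do not say so. They say that results are divided by arm and give a convention for reading a mean; the comparison of winners is the reader's own step.

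A reader might also infer that no between-arm comparison exists for these items. That is not supported either. The scores are analysed as means, so the general t-test or Mann-Whitney rule plausibly covers them and would give a spread and a test per item. This stands, with two limits. The plan does not class the scores as continuous, and the Mann-Whitney branch would report medians where the Questionnaire section asks for means. More importantly, a test of one item between arms does not say whether item A outranks item B among the same women, which is what the rule asserts.

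A third tempting reading is that false differences between arms will be frequent. That depends entirely on how close the leaders are. Under one SD and correlation the chance runs from under 1% to 83%, and nothing in the documents says where this trial lies. Nor does the rule always produce a single winner, since exact ties can occur.

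Finally, these items are descriptive and are not a named outcome. That limits the weight of the point. It does not remove it, because the plan itself supplies a conclusion rule for them.

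**Conclusion.** The point holds in a narrow, conditional form. The plan states a rule for what is most important and plans no analysis of whether the top item really leads within an arm. When the leaders are within about 0.2 points, the rule names the wrong item in roughly 18 to 39% of arms, and arms with identical priorities disagree roughly 30 to 54% of the time. Once the lead reaches 0.5 points, disagreement falls to about 2%. These figures rest on the assumed SD of 1.2, correlation of 0.3, item means and item counts; larger SDs or forced ranking would change them. The documents do not support saying that the arms will often differ by chance, or that a changed top item is planned as evidence of a counselling effect. The primary outcome and sample size are untouched. The change is still worth making, because it alters what may be concluded from these questions at very little cost.

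**What to change.** Replace the rule in the Questionnaire section with text along these lines: *Each item is reported by arm as a mean with 95% CI. Within each arm, the within-woman difference between the top and next-highest items is reported with its 95% CI. If that interval includes 0, the leading items are described as not separated. Any effect of counselling on priorities is judged from the between-arm mean difference (95% CI) for each item, not from a change in top item.*

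Statistical analysis should also say whether the 1-5 and 1-6 scores fall under its rule for continuous data, so that the instruction to use means and the possible switch to medians do not conflict.

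The cost is a few lines of analysis on data already being collected, with no extra women or questions. The downside is that some results will be reported as tied where the present rule would give one answer.
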